8.1.3 Dose and Regimen

This is a placebo-controlled, double-blind, parallel group study comparing AD-4833 SR 0.8 mg Tablet to Placebo. Subjects will be randomized in a blinded fashion to one of the following within the following two subject groups, Non-Hispanic/Latino Caucasian and Non-Caucasian or Hispanic/Latino Caucasian.

Table 8.a describes the dose and tablet count that will be provided to each group.

Table 8.a Sponsor-Supplied Drug

Treatment Group	Dose	Treatment Description	
		Active	Placebo
1	Placebo QD	Zero active tablets	One AD-4833 tablet placebo
2	AD-4833 SR 0.8 mg Tablet QD	One AD-4833 SR 0.8 mg tablet	Zero placebo tablets

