13.1.3 Efficacy Analysis

There are 2 independent null hypotheses in this protocol: (1) assumes that there is no difference in conversion rate between the placebo-treated high-risk and low-risk groups as defined by the prognostic biomarker test and (2) assumes that there is no difference in conversion rate between the high-risk active- and placebo-treated subjects. The alternate hypotheses are: (1) there is a difference between the high- and low-risk groups treated with placebo, and (2) there is a difference between placebo and active treatment in the high-risk group.

In order to test the first hypothesis, a test from a Cox proportional hazards survival model will be used to compare data from non-Hispanic/Latino Caucasians in the (placebo-treated) low-risk group (ie, the combined placebo groups) with data from non-Hispanic/Latino Caucasians in the placebo-treated subjects in the high-risk group. The event in this analysis will be the diagnosis of cognitive impairment. If this test is significant at the 0.01 level, it can be concluded that the diagnostic prognostic test has differentiated between subjects at low and high risk of being diagnosed with cognitive impairment within 5 years of taking the test.

A similar analysis will be used to compare the placebo- and active-treated non-Hispanic/Latino Caucasian subjects within the high-risk group. If this test is significant at the 0.01 level, it can be concluded that active treatment has delayed the development of cognitive impairment within the 5-year period.

A secondary all-comers analysis will be done to compare the placebo and active-treated subjects within the high-risk group.

CONFIDENTIAL

All data collected in the study will be listed and summarized either by mean, SD, median, and range or by frequency tables, as appropriate to the data.

Time-to-event data will be analyzed using a Cox proportional hazard model, including an investigation of the effects of covariates (testing center, age, sex, etc). The incidence of MCI due to AD will also be compared using a chi-squared test and the difference in incidence will be reported along with 95% confidence intervals.

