In addition to the primary analysis population, it is anticipated that approximately 5% as many subjects will be Hispanic/Latino and/or non-Caucasian. Additional analyses for Hispanic/Latino and/or non-Caucasian subjects and for all subjects will be done to support the results of the primary analysis. These analyses will be the same as those conducted for the primary subgroup of the Caucasian subjects in order to evaluate the biomarker effectiveness within this extra subpopulation and the efficacy for pioglitazone within high-risk non-Caucasian subjects.

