 - Approximately 314 subjects in the low-risk group: All subjects stratified to the low-risk stratum will also be randomized to maintain the stratification blind, but all subjects in this stratum will receive placebo.

- Non-Caucasian subjects and Hispanic/Latino Caucasian subjects. Subjects will be allocated to risk strata using the same algorithm as for the non-Hispanic/Latino Caucasian subjects.

Since all subjects screened at the time of Amendment 5 will be allowed to randomize if they continue to meet all eligibility criteria, it is estimated that approximately 3,500 will be randomized with the following groups:

- Non-Hispanic/Latino Caucasian subjects. Estimated 3,330 subjects further divided into:
 - Approximately 2,940 subjects in the high-risk group (pioglitazone, n=1,470; placebo, n=1,470).
 - Approximately 394 subjects in the low-risk group: All subjects stratified to the low-risk stratum will also be randomized to maintain the stratification blind, but all subjects in this stratum will receive placebo.
- Non-Caucasian subjects and Hispanic/Latino Caucasian subjects. Subjects will be allocated to risk strata using the same algorithm as for the non-Hispanic/Latino Caucasian subjects (n=167).

Because the data used to develop the biomarker risk algorithm was collected in non-Hispanic/Latino Caucasian subjects only, biomarker qualification will be based upon non-Hispanic/Latino Caucasian subjects in the placebo arm of the high-risk stratum compared to data from non-Hispanic/Latino Caucasian subjects in the low-risk stratum. Likewise, the primary analyses to evaluate the effects of pioglitazone versus placebo will be within the non-Hispanic/Latino Caucasian high-risk sub-group. CCI

An interactive response system will be used for central randomization. Stratification status and treatment assignment of all study participants will be double-blind. The randomization will be stratified based on participation in the vMRI substudy (approximately 300 subjects).

For subjects who are not participating in the vMRI substudy, subjects in the high-risk stratum will be randomized to pioglitazone and placebo in a 1:1 ratio. Subjects in the low-risk stratum will be randomized only to placebo.

For subjects who are participating in the vMRI substudy, subjects in the high-risk stratum will be randomized to pioglitazone and placebo in a 5:4 ratio. Subjects in the low-risk stratum will be randomized only to placebo.

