9.9 Efficacy Analyses

Except as otherwise noted, the analyses and summaries will be based on the FAS.

All primary and key secondary efficacy analyses and summaries will be presented separately for the following groups of subjects:

- Non-Hispanic/Latino Caucasian subjects.
- Hispanic/Latino and/or non-Caucasian subjects.
- All subjects.

All primary, secondary, additional, and other outcomes variables listed below will be presented by treatment group using descriptive statistics by visit (including change-from-baseline for continuous variables) and presented in efficacy listings.

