9.9.3.1 Primary biomarker risk assignment algorithm analysis

In order to test the first hypothesis, a test from a Cox proportional hazards survival model will be used to compare data from non-Hispanic/Latino Caucasian subjects in the (placebo-treated) low-risk group (ie, the combined placebo groups) with data from non-Hispanic/Latino Caucasian subjects in the placebo-treated subjects in the high-risk group. The event in this analysis will be an adjudicated event of MCI due to AD (see Section 9.9.4 below). If this test is significant at the 0.01 level, it can be concluded that the diagnostic prognostic test has differentiated between subjects at low and high risk of being diagnosed with MCI due to AD within 5 years of taking the test.

An exact partial likelihood function will be constructed to fit the Cox proportional hazards (CPH) model to accommodate events with the same times to the event. The robust sandwich estimate for the covariance matrix from the CPH model will be used. The analysis of the primary biomarker comparison will be conducted using the FAS and a CPH model of MCI due to AD events with a factor for biomarker risk assignment and including center, gender, and education as covariates. (Except as otherwise noted, education will be treated as a continuous variable and measured in years for purposes of statistical modeling.)

Parameter estimates, 2-sided 99% CIs, and appropriate p-values for the hazard ratios obtained from the CPH model will be computed to test the null hypothesis of equality of the hazard functions between high-risk placebo and low-risk placebo.

Assessment of the proportional hazards assumption for risk assignment category will be assessed. Plots of Schoenfeld residuals obtained from the CPH models that fit the primary MCI-to-AD endpoint versus ordered time of events along with a smoothing spline will be used to evaluate the proportional hazards assumption for risk assignment category. Systematic departures from a horizontal line are indicative of meaningfully non-proportional hazards. Diagnostic checks will be presented in CSR Appendix 16.1.9.

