9.9.3.2 Primary efficacy analysis

A similar analysis process as described above for the primary biomarker risk algorithm analysis will be used to compare the placebo- and active-treated non-Hispanic/Latino Caucasian subjects within the high-risk group (ie, using a similar CPH model with covariates of center, gender, and education and an additional covariate of age but using a factor of high-risk treatment group instead of biomarker risk assignment). If this test is significant at the 0.01 level, it can be concluded that active treatment has delayed the development of mild cognitive impairment due to AD.

An exact partial likelihood function will be constructed to fit the Cox proportional hazards (CPH) model to accommodate events with the same times to the event. The robust sandwich estimate for the covariance matrix from the CPH model will be used. The analysis of the primary efficacy comparison will be conducted using the FAS and a CPH model of MCI due to AD events with a factor for treatment and including center, gender, education, and age as covariates.

Parameter estimates, 2-sided 99% CIs, and appropriate p-values for the hazard ratios obtained from the CPH model will be computed to test the null hypothesis of equality of the hazard functions between the high-risk pioglitazone and high-risk placebo treatment groups.

Assessment of the proportional hazards assumption for treatment group will be assessed. Plots of Schoenfeld residuals obtained from the CPH models that fit the primary MCI-to-AD endpoint versus ordered time of events along with a smoothing spline will be used to evaluate the proportional hazards assumption for treatment group. Systematic departures from a horizontal line are indicative of meaningfully non-proportional hazards. Diagnostic checks will be presented in CSR Appendix 16.1.9.

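### The all-subjects analyses pool two race/ethnicity groups with no term for them, and the protocol and SAP disagree on whether the groups are randomisation strata: a small, conditional effect on the supportive biomarker hazard ratio only

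*Protocol*

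**What the plan says.** **Randomisation.** Protocol 8.1.3 describes randomisation "within the following two subject groups, Non-Hispanic/Latino Caucasian and Non-Caucasian or Hispanic/Latino Caucasian". Protocol 6.1 and 8.3 list expected numbers by the same two groups. SAP 6.4 gives a different factor: "The randomization will be stratified based on participation in the vMRI substudy (approximately 300 subjects". It does not mention race/ethnicity as a stratum.

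**Pooled analyses.** Protocol 13.1.3 plans an all-comers efficacy comparison: "A secondary all-comers analysis will be done to compare the placebo and active-treated subjects within the high-risk group". It also plans analyses in the other race/ethnicity group and in all subjects, for the biomarker as well as for efficacy, and says: "These analyses will be the same as those conducted for the primary subgroup". SAP 9.9 states: "All primary and key secondary efficacy analyses and summaries will be presented separately for the following groups of subjects". The groups it lists are non-Hispanic/Latino Caucasian subjects, the others, and everyone. SAP 9.9.3.5 includes an all-subjects run of both the efficacy and the biomarker comparison.

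**Model terms.** The biomarker Cox model is fitted "with a factor for biomarker risk assignment and including center, gender, and education as covariates" (SAP 9.9.3.1). The efficacy Cox model is fitted "with a factor for treatment and including center, gender, education, and age as covariates" (SAP 9.9.3.2). The log-rank sensitivity tests are stratified by gender only (SAP 9.9.3.4). The key secondary MMRM in SAP 9.9.6 has no race/ethnicity effect.

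**The concern.** These models suit the primary population, which is a single race/ethnicity group. When they are reused on pooled data, two things follow.

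For efficacy, if Protocol 8.1.3 is right about the strata, the pooled analysis leaves out a randomisation factor.

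For the biomarker, risk status is assigned by genotype and age rather than randomised, and Protocol 6.1 says the algorithm was developed in non-Hispanic/Latino Caucasian data only. If the other group has both a different share of low-risk subjects and a different conversion rate, part of the pooled high-versus-low contrast reflects group membership. The pooled biomarker HR could then differ from the primary one even though the algorithm separates risk equally well in both groups. At stake is how a supportive result is read, not either primary conclusion.

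**Working it through.** **The plan's own figure.** With 15% and 9% over 5 years, HR = ln(0.91)/ln(0.85) = 0.580. Schoenfeld's formula at two-sided alpha 0.01 and 90% power gives 4 × (2.576 + 1.282)² / (ln 0.580)² = 201 events, against 202 stated. The planning rates are therefore used below.

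**Inputs from the documents**
- Non-Hispanic/Latino Caucasian: 1,470 high-risk placebo and 394 low-risk, out of 2,940 high-risk in total (Protocol 6.1). Low-risk share 394/3,334 = 11.8%.
- Other group: 167 subjects (Protocol 6.1). Risk split and conversion rate are not given.
- 5-year conversion 15% high-risk and 4% low-risk; dropout 12% a year (Protocol 13.3).
- At least 60% low-risk at screening, thinned by random rejection (SAP 6.4; Protocol 8.3 also describes an allocation scheme for low-risk subjects).

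**Assumptions.** Exponential times; 4.5 years' follow-up; the same true HR in both groups; other-group high-risk subjects split 1:1; hazard in the other group *m* = 0.5 to 2 times that of the main group; no adjustment for center, gender or education.

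**Hazards.** High-risk -ln(0.85)/5 = 0.0325; low-risk -ln(0.96)/5 = 0.00816; dropout -ln(0.88) = 0.1278. True HR = 0.0325/0.00816 = 3.98.

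**Plausible low-risk share.** With 60% low-risk at screening, the acceptance of low-risk relative to high-risk subjects is (394/2,940)/(60/40) = 0.089. If the same acceptance applies to the other group, a screening share *s* gives randomised odds of 0.089 × s/(1-s):
- s = 40%: odds 0.060, share 5.6%
- s = 80%: odds 0.357, share 26.3%

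In reverse, a randomised share of 25%, 40% or 60% would need about 79%, 88% or 94% low-risk at screening.

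**Pooled biomarker HR.** Person-years per subject are g(λ) = [1 - exp(-(λ + 0.1278) × 4.5)]/(λ + 0.1278), and the pooled HR is the ratio of pooled event rates. Example with m = 2 and a 26.3% low-risk share (44.0 low-risk, 61.5 high-risk placebo):
- High-risk: events 153.2 + 12.0 = 165.2; person-years 4,712 + 185 = 4,897; rate 0.03373
- Low-risk: events 10.8 + 2.4 = 13.2; person-years 1,326 + 146 = 1,472; rate 0.00897
- HR = 0.03373/0.00897 = 3.76, which is 0.944 of 3.98

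| Low-risk share in the 167 | m = 0.5 | m = 2 |
|---|---|---|
| 5.6% | 3.92 (-1%) | 4.08 (+2%) |
| 11.8% (as main group) | 3.98 (0%) | 3.97 (0%) |
| 25% | 4.09 (+3%) | 3.78 (-5%) |
| 26.3% | 4.11 (+3%) | 3.76 (-6%) |
| 40% | 4.22 (+6%) | 3.59 (-10%) |
| 60% | 4.38 (+10%) | 3.39 (-15%) |

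With m = 1 the HR is 3.98 at every share. Both factors must differ for a shift to occur.

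**Against sampling error.** In the example, SE(log HR) is about √(1/165.2 + 1/13.2) = 0.29. The shift is ln(0.944) = -0.057, or 0.2 SE. At a 60% share and m = 2 there are 159.7 and 16.2 events, SE = 0.26, and the shift is ln(0.851) = -0.162, or 0.6 SE.

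**Check by another route.** The large-sample limit of the Cox estimate over 5 years gives the same pattern: 4.30 (+8%) and 3.48 (-13%) at a 50% share, and 4.46 (+12%) and 3.30 (-17%) at 70%, for m = 0.5 and 2. Outside the stated hazard range shifts are larger: m = 3 with a 70% low-risk share gives 2.84 (-29%). In every scenario tried, up to m = 3 with all 167 subjects low-risk, z is at least 4.38 against a threshold of 2.576.

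**Efficacy.** The Cox limit with 1:1 allocation in each group gives a pooled HR of 0.580 to 0.583 against 0.580 for m between 0.5 and 3, a shift of at most 0.4%.

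**The case against.** The case for leaving the plan alone is substantial.

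- *Separate presentation.* SAP 9.9 shows each group beside the pooled result, so a difference would be visible. This limits the consequence but does not correct the pooled estimate. The other group is also too small to explain a shift: at an 11.8% low-risk share and equal hazard it has about 20 low-risk subjects and 0.5 expected low-risk events.
- *The unadjusted HR is a legitimate target.* For a prognostic test one may want to know how well the label separates risk among everyone tested, and confounding is then the wrong word. This stands as a choice of estimand, but the plan does not say that it makes that choice.
- *Stratifying assumes a common HR,* which is itself an open question outside the main group. This stands, so the change is not free of drawbacks.
- *Center and education are in the model* and may absorb part of the shift. This stands and cannot be quantified from the documents. Part of SAP 9.9.3.5 is redacted, so further subgroup modelling cannot be excluded.

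A reader might infer more than the documents support:
- *That the primary results are confounded.* They are not, because both are confined to one group.
- *That the all-comers efficacy comparison is invalid because it is not analysed as randomised.* That rests on one sentence in a dosing section, which SAP 6.4 does not repeat, and the effect on the HR is under 0.5%.
- *That a 10-15% shift is to be expected.* It needs about 94% low-risk at screening if the rejection scheme works equally in both groups. No passage exempts either group, although the details are in an IWRS document outside these files.
- *That the pooled runs are meant to extend the claims to other groups.* Protocol 13.1.3 gives them the role of supporting the primary analysis, and Protocol 6.1 calls the other group's data limited and exploratory.

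**Conclusion.** The point holds as a minor one. The two documents do not agree on the randomisation strata, and the all-subjects analyses omit the race/ethnicity group. The primary analyses and, for practical purposes, the pooled efficacy HR are untouched.

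Only the supportive all-subjects biomarker HR can move, and only if low-risk share and conversion rate both differ in about 5% of subjects (167/3,500). Assuming half to twice the hazard, the shift is about -6% to +3% for a randomised low-risk share of 6-26%, at most about 0.2 SE. It grows to about -15% to +10% at a 60% share. The significance of the biomarker test is unchanged in all cases under the planning rates. The hazard range, the shares and the equal working of the rejection scheme are assumptions.

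**What to change.** For the all-subjects analyses only:
- stratify the Cox models and the log-rank tests by non-Hispanic/Latino Caucasian versus other;
- include the same group as a fixed effect in the key secondary MMRM;
- keep the separate-group presentations of SAP 9.9.

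Reconcile SAP 6.4 with Protocol 8.1.3 so that both state the randomisation strata actually used.

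The cost is a sentence or two in the SAP before unblinding and one STRATA or class variable. The non-Hispanic/Latino Caucasian determination is already a baseline characteristic in SAP 9.5. There is a small downside: the stratified estimate assumes one HR across both groups, and the small stratum adds so little information that the result will lie close to the primary one.

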8.1.4 Overdose

An overdose is defined as a **known** deliberate or accidental administration of investigational drug, to or by a study subject, at a dose above that which is assigned to that individual subject according to the study protocol.

All cases of overdose (with or without associated adverse events) will be documented on an Overdose page of the (e)CRF, in order to capture this important safety information consistently in the database. Adverse events associated with an overdose will be documented on AE CRF(s) according to Section 10.0, PTEs and AEs.

Serious adverse events of overdose should be reported according to the procedure outlined in Section 10.2.2, Collection and Reporting of SAEs.

In the event of drug overdose, the subject should be treated symptomatically. In the event of deliberate or accidental drug overdose, general symptomatic and supportive measures should be used.

8.2 Investigational Drug Assignment and Dispensing Procedures

The investigator or investigator's designee will access the IWRS at Screening to obtain the subject study number. The investigator or the investigator's designee will utilize the IWRS to randomize each qualified subject into the study at Visit 3. During this contact, the investigator or designee will provide the necessary subject-identifying information, including the subject number assigned at screening.

The investigator or investigator's designee will access the IWRS at each dispensing visit to obtain medication identification numbers (Med IDs) for up to two bottles containing 100 tablets

each of either AD-4833 SR 0.8 mg or placebo based on the subject's randomized treatment arm. Subjects will be instructed to take 1 tablet per day, orally, at the same time of day, preferably in the morning, or as directed. Take with or without food. Study drug is to be kept in the container provided until the dose is to be taken. The first dose is to be taken the morning after the randomization visit. The investigator or investigator's designee will utilize the IWRS for Med ID assignment at every subsequent dispensing visit. If sponsor-supplied drug AD-4833 SR 0.8 mg Tablets or placebo is lost or damaged, the site can request a replacement from the IWRS. (Refer to the IWRS manual provided separately.)

The investigator must maintain records of all sponsor-supplied drug delivery to the site. The site will receive a confirmation email from the IWRS providing the Med ID's assigned at each dispensing visit. The site will print, date and initial the email and file in the subject's file as documentation of correct dispensing. The investigator or designee will maintain records of site inventory, dispensation and use by each subject, and return of investigational medicinal product (IMP) to the sponsor or designee. Drug supplies will be counted and reconciled at the site before being returned to the sponsor or designee.

8.3 Randomization Code Creation and Storage

Randomization personnel of the sponsor or designee will generate the randomization schedule and will provide it to the IWRS vendor prior to the start of this study. All randomization information will be stored in a secured area, accessible only by authorized personnel.

Based on statistical requirement, a minimum of 2,793 subjects will be stratified into high- and low-risk groups (for the development of MCI due to AD over the next 5 years) based upon the results of the biomarker risk algorithm. Subjects will be randomized into this study as follows:

- Non-Hispanic/Latino Caucasian subjects. Approximately 2,660 subjects further divided into:
 - Approximately 2,346 subjects in the high-risk group (pioglitazone n=1,173; placebo n=1,173).
 - Approximately 314 subjects in the low-risk group: All subjects stratified to the low-risk stratum will also be randomized to maintain the stratification blind, but all subjects in this stratum will receive placebo.
- Non-Caucasian and Hispanic/Latino Caucasian subjects: Subjects will be allocated to strata using the same algorithm as for the non-Hispanic/Latino Caucasian subjects.

Since all subjects screened at the time of Amendment 5 will be allowed to randomize if they continue to meet all eligibility criteria, it is estimated that approximately 3,500 will be randomized with the following groups:

- Non-Hispanic/Latino Caucasian subjects. Estimated 3,330 subjects further divided into:
 - Approximately 2,940 subjects in the high-risk group (pioglitazone, n=1,470; placebo, n=1,470).

CONFIDENTIAL

- Approximately 394 subjects in the low-risk group: All subjects stratified to the low-risk stratum will also be randomized to maintain the stratification blind, but all subjects in this stratum will receive placebo.
- Non-Caucasian subjects and Hispanic/Latino Caucasian subjects. Subjects will be allocated to risk strata using the same algorithm as for the non-Hispanic/Latino Caucasian subjects (n=167).

It is anticipated that at least as many low-risk subjects will be available for screening as high-risk subjects. Since only 314 low-risk subjects are needed, low-risk subjects who pass all other eligibility criteria and are eligible to enter the study will only be randomized into the study if the requirements for a pre-specified allocation scheme are met. This scheme is designed to ensure that low-risk subjects are enrolled throughout the whole duration of the study enrollment period and it is detailed in the IWRS specifications.

